All undergraduate student interns/volunteers involved in this project have completed all required trainings for handling biological specimens for humans, and have been trained by the PI and graduate students for each specific procedure (e.g., centrifugation, pipetting, sample storage). They will not perform any procedure that is invasive (e.g., microneurography) or requires a high degree of technical skill (e.g., Doppler ultrasonography). In addition, they will have limited direct interaction with participants. Undergraduate student interns/volunteers mostly function in a supporting role and assist all aspects of the study [e.g., controlling the data acquisition computer, which is a task that requires being present for the duration of the experiment (~4 hrs) but does not require undergraduate students (usually) to ever physically touch the participant or speak to them].

4. Special Populations

Does this project involve any of the following:

Research on Children?

no

Research with Prisoners?

no

If yes, complete the Prisoners in Research Form and upload to IRBNet as supporting documentation

Research with Pregnant Women?

no

Research with any other vulnerable population (e.g. cognitively impaired, economically disadvantaged, etc.)? please describe

Adults with major depressive disorder (MDD; unmedicated)

We and others have demonstrated that peripheral endothelial dysfunction, mediated in part by a loss of nitric oxide (NO) bioavailability and function, is evident in young/middle-aged adults with MDD but otherwise free of CVD risk factors. However, the upstream mediators remain unclear. Inflammation and mitochondrial redox homeostasis are known to regulate NO bioavailability, and intriguingly, both are disrupted in MDD. Importantly, psychosocial stress can also trigger proinflammatory cytokine production and mitochondrial dysfunction. However, whether and how daily stress influences inflammation and mitochondrial redox balance, and the degree to which this translates to vascular dysfunction, in adults with MDD remains unclear. Daily stress is also associated with impairments in current cognitive performance and increased risk of future cognitive decline, but the mechanisms remain incompletely understood.

Aim 1: To determine if the links between daily stress and 1) proinflammatory cytokine production and 2) mitochondrial redox balance are sensitized in young-to-middle aged adults with MDD.

Aim 2: To determine the link between daily stress and peripheral endothelial function in young-to-middle aged adults with MDD.

[figure not shown]
Aim 3: To explore the complex interactions between daily stress, redox-immunological-vascular function, and daily cognitive function in young-to-middle aged adults with MDD.

6. PROCEDURES Describe all procedures involving human subjects for this protocol. Include copies of all surveys and research measures.

This is a cross-sectional study. Two subject groups will be recruited: 1) non-depressed healthy adults (HA) will have no evidence of current or lifetime history of major psychiatric illness and 2) unmedicated adults with MDD will meet the Diagnostic and Statistical Manual of Mental Disorders (DSM-5) diagnostic criteria for MDD.

Below is a detailed description of all techniques and measurements to be utilized and/or obtained, as well as a complete description of the experimental protocol (see schematic illustration below). First, all participants will complete an in-person screening/familiarization visit (~1.5 hours) to determine eligibility. Thereafter, each participant will complete two 15-day measurement bursts (hereafter referred to as "testing cycles"). Micro-longitudinal measurement burst/testing cycle designs consist of repeated sequences of closely spaced assessments that provide multiple time scales, allowing for the examination of processes unfolding within an individual over short time periods (e.g., days) as well as how these change over longer time intervals (e.g., months). Each 15-day testing cycle consists of 1) an ambulatory assessment of daily stress processes and cognitive function for 14 consecutive days (~2-3 hours in total), 2) daily wrist accelerometry for 14

consecutive days (no additional time burden), 3) daily saliva collection for 4 consecutive days (~1 hour in total), and 4) an experimental visit to assess vascular endothelial function (~6 hours). The two cycles will be separated by ~3-6 months; the lack of standardization of the timing between cycles is purposeful, as it will allow us to begin to more precisely disentangle the temporal patterning of the proposed relations both within- and between-subjects. This protocol is illustrated below:

Pre-Screening: Initial Interview/Survey to Determine Eligibility

Interested people may contact us. The script of the study information (see attached document "Study Information") will be provided verbally (if initial contact is by phone) or in writing (if initial contact is by email). During this initial contact, we also conduct a basic interview/survey to determine whether the participant is likely to meet study eligibility criteria (see attached document "Pre-Screening Survey"). Responses will either be recorded by a study team member (if initial contact is by phone) or electronically via REDCap (if initial contact is by email). Based on historical experience in our laboratory, we anticipate that the vast majority of these initial interviews will occur electronically; therefore, the attached Pre-Screening Survey is formatted for electronic administration. If the initial contact is by telephone, these interview questions will be read verbatim to participants; such telephone interviews will occur in a private office space and written responses will be documented.

This interview includes basic demographic information [name, phone number, email address, age and date of birth, preferred contact method, sex and gender, etc.] and a brief assessment of general health [height/weight, medications taken regularly, health history (e.g., any known diseases), history of tobacco use, etc.]. During this interview, potential participants will also complete the PROMIS Emotional Distress-Depression Short Form (these questions are embedded within the pre-screening survey). This scale can be administered over the phone or electronically. A raw PROMIS score > 18 is indicative of mild depressive symptoms. The PROMIS is used to "pre-screen" adults for depressive symptoms and thus limits the burden of scheduling and conducting screening visits in patients who are ultimately not likely to meet all eligibility criteria. Given the relative ease of recruiting non-depressed healthy adults into our research study, conducting the PROMIS prior to the on-site screening visit allows us to further target the patient population of interest. *This initial interview to determine eligibility presents no more than minimal risk of harm to subjects and involve no procedures for which written consent is normally required outside of the research context.*

If, after completion of this initial interview to determine study eligibility, the subject appears to meet inclusion criteria and is interested in enrolling, we will schedule a screening visit (see below for details). If enrolled, the interview responses will be coded with a unique subject number. Pre-screening 'failures' will be tracked for date of contact and reason for ineligibility; however, if not

enrolled, all pre-screening information will be de-identified and destroyed.

Screening/Familiarization Laboratory Visit

Note: All participants who attend this laboratory visit, regardless of continued enrollment or subject group, will be given materials on local resources for counseling/psychiatric care and crisis/suicide hotline information (created and published by the UD Center for Counseling and Student Development; this document outlines resources available to both students and non-students and includes resources available on- and off-campus), as well information published by the National Institute of Mental Health regarding symptoms of depression, anxiety, and suicidality (see attached document "Mental Health Resources"). If, at any time, a participant expresses active suicidal or homicidal ideation with intent to harm, an approved crisis protocol for immediate clinical evaluation will be implemented (see attached document "Crisis Protocol"). This safety plan was developed in consultation with [name], EDD, APRN, PMHCNS-BC and licensed clinical psychologist [name]. As psychiatric mental health advanced practice registered nurses, both [name] and [name] will provide psychiatric clinical oversight for the management of adults with MDD.

1. The participant electronically signs the informed consent before screening procedures begin using REDCap's eConsent framework. During the eConsent, the participant will take control of the screen so that they can digitally initial and sign the consent using their finger. After the participant signs the consent, they will receive a digital copy of the signed consent via email. Paper versions will be available for any participants who prefer a physical copy. Signed paper consents will be scanned and uploaded to REDCap; the hard paper copy will be shredded.
2. Participants provide contact information (see attached document "Contact Information") and complete a standardized general health history (see attached document "Medical History Form").
3. Because of the heterogeneity in the hormonal milieu of participants in the proposed age ranges, females and males will complete separate questionnaires to assess symptoms of reproductive aging (see attached documents "Females.Gyno+Meno" and "Males.AMS").
4. The investigator measures height (stadiometer), weight (digital scale), waist circumference (tape measure), seated blood pressure (Welch Allyn Connex), seated heart rate (Welch Allyn Connex), and temperature (Welch Allyn SureTemp Plus).
5. Women will provide a urine sample for a pregnancy test.
6. [name] or a trained investigator administers the Mini International Neuropsychiatric Interview (MINI) to determine depression status (see attached document "MINI"). The MINI has 16 sections and takes ~30 minutes to complete. During the neuropsychiatric interview, participants will be advised that they are able to stop the interview at any time or not answer questions if preferred.
 - The investigators provide all participants, regardless of neuropsychiatric interview responses or subject group assignment, with materials on local resources for counseling/psychiatric care and crisis/suicide hotline information (created and published by the UD Center for Counseling and Student Development; this document outlines resources available to both students and non-students and includes resources available on- and off-campus), as well information published by the National Institute of Mental Health regarding symptoms of depression, anxiety, and suicidality (see attached document "Mental Health Resources").
 - If a participant indicates a current or lifetime history of major psychiatric illness aside from MDD, we will provide them with the Mental Health Resources document, strongly encourage them to follow-up with a clinician, and exclude them from the study.
7. [name] or a trained investigator administers the Columbia-Suicide Severity Rating Scale (C-SSRS) to assess suicidality (see attached document "C-SSRS Triage"). This scale was developed in partnership with the National Institute of Mental Health and has been validated

across many settings, including for use in biomedical research. It is an assessment tool that evaluates suicidal ideation and behavior and will help establish a subject's immediate risk of suicide and will be used as a criterion to evaluate acute suicide risk. Training is available before administering the C-SSRS (see attached document "C-SSRS.[name] completion certificate"). The C-SSRS takes <5 minutes to administer. Per existing Clinical Practice Guidelines, the presence of active current suicidal ideation with intent ("yes" to item 4) or a specific plan ("yes" to item 5) or active current suicidal behavior with a preparatory attempt ("yes" to item 6) will trigger the Crisis Intervention Protocol (see attached document "Crisis Protocol"). *The presence of suicidal ideation without intent will not trigger any additional assessments, as Clinical Practice Guidelines consider this to be low acute risk.*

8. Trained research personnel administer a battery of standardized cognitive function assessments on a tablet device. This assessment takes ~30 minutes. This will entail several computerized tests that assess major cognitive subdomains, including processing speed (e.g., Pattern Comparison Processing Speed Test), executive function (e.g., Dimensional Change Card Sort Test; Flanker Inhibitory Control and Attention Test), working memory (e.g., List Sorting Working Memory Test), episodic memory (e.g., Picture Sequence Memory test), and language (e.g., Picture Vocabulary Test; Oral Reading Recognition Test). These measures capture key cognitive processes known to impact daily function. Participants will also complete the NIH Patient-Reported Outcomes Measurement Information System (PROMIS) to assess self-reported cognitive function (see attached document "PROMIS Cognition").

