7. STUDY POPULATION AND RECRUITMENT

Describe who and how many subjects will be invited to participate. Include age, gender and other pertinent information.

- 18 – 55 yrs

- Males and females
 - 60 non-depressed healthy adults will have no evidence of current or lifetime history of major psychiatric illness, assessed by the MINI and self-report
 - 60 unmedicated adults with MDD will meet the DSM-5 criteria for MDD, assessed by the MINI and self-report; participants with co-morbid anxiety, stress, and trauma-related disorders will be included if MDD is the primary diagnosis
 - 30 selective serotonin reuptake inhibitor (SSRI)-treated (current monotherapy) adults with MDD will meet the DSM-5 criteria for MDD, assessed by the MINI and self-report; participants with co-morbid anxiety, stress, and trauma-related disorders will be included if MDD is the primary diagnosis

Subjects will be recruited from the University of Delaware and surrounding local communities. We use recruiting methods that will reach a large percent of the general population. We advertise for subjects, and interested persons contact us. We post recruitment flyers in various campus (e.g., student union, classroom building bulletin boards, dormitory bulletin boards, campus eateries, etc.) and community (e.g., coffee shops, bookstores, local businesses, etc) locations. We will obtain permission to provide recruitment flyers to local medical and wellness practices (family physicians, mental healthcare providers/specialists, etc.) and other locations specifically targeted to recruit patients with depression (e.g., Center for Counseling & Student Development). Additionally, the text from the fliers may be utilized in “word of mouth” recruiting if the opportunity presents itself. Recruitment may also occur via online social media resources (e.g., Instagram, Twitter, Google, Craig’s List, NextDoor, Facebook, ResearchMatch.com, etc.), as well as in campus newsletters and local newspapers/mailings.

Attach all recruitment fliers, letters, or other recruitment materials to be used. If verbal recruitment will be used, please attach a script.

Advertisements

- Study Information.svcMDD.20240118
- CHS ad
- gen.recruit.ad.bookmark
- gen.recruit.ad.buisinesscard
- recruit general.unMDD_1
- recruit general.unMDD_2
- CPP Recruitment EDDM Postcard
- svcMDD.research match.20240701

Describe what exclusionary criteria, if any will be applied.

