The exclusion criteria are applied to all groups. We will not enroll non-English-speaking individuals. This protocol involves the use of numerous questionnaires, including a detailed neuropsychiatric interview with the investigators. In addition, participants need to understand English to follow instructions and comply with procedures conducted during the screening and experimental visits.

Subjects will be excluded at the discretion of PI/collaborating psychiatrist/examining clinician or for any of the following reasons:

- Psychiatric illness aside from MDD (e.g., bipolar disorder, schizophrenia, eating disorders), assessed by the MINI and self-report
- Active current suicidal ideation with intent or a specific plan, assessed by the Columbia-Suicide Severity Rating Scale
- Active current suicidal behavior with a preparatory attempt, assessed by the Columbia-Suicide

Severity Rating Scale

- Active substance dependence, assessed by the MINI
- Current or recent (within 8 wks) use of medications that could conceivably alter neural-cardiovascular-immunological function [including (but not limited to) antihypertensives and HMG-CoA reductase inhibitors] or psychoactive or psychopharmacological drugs aside from SSRIs [including (but not limited to) antidepressants, antipsychotics, benzodiazepines, mood stabilizers, sedatives/hypnotics, dopaminergic agents, stimulants, buspirone, and triptans]
- Changes or alterations in medication status (starting a new, additional, or different medication or changing the dose of a current medication)
- Unstable or diagnosed chronic clinical disease, including cardiovascular, metabolic, renal, hepatic, autonomic, autoimmune, or dermatological disease (e.g., hypertension, heart disease, diabetes, hyperlipidemia, psoriasis)
- Body mass index <18.5 or >35 kg/m²
- Tobacco or nicotine use, including vaping and electronic cigarettes
- Pregnancy (including a positive urine pregnancy test) or breast-feeding
- Lack of access to a device with internet connectivity
- Known allergies to pharmacological agents/drugs

Describe what (if any) conditions will result in PI termination of subject participation.

Subjects will be terminated from participation if it is believed that such participation endangers their welfare or for an inability to comply with study procedures.

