8. RISKS AND BENEFITS

List all potential physical, psychological, social, financial or legal risks to subjects (risks listed here should be included on the consent form).

Neuropsychiatric Interview and Depressive Symptom Severity/Suicidality Assessments

- General: There is risk that adults with MDD will experience clinical worsening.

Mitigation: We have robust standard operating procedures in place to ensure the safety of participants. In no case will a participant be denied necessary medical or psychiatric treatment for reasons related to study participation. No patients with MDD who are currently treated with antidepressant pharmacotherapy will be asked or allowed to discontinue to participate. We have multiple screening and crisis protocols in place to ensure patient safety and compliance with study procedures. Psychiatric mental health advanced practice registered nurses and a licensed clinical psychologist will provide psychiatric clinical oversight for the management of adults with MDD. Our crisis intervention plan allows for rapid referral, including immediate referral for acute psychiatric issues (described below and in accompanying documents). This crisis protocol can be triggered at any time and at the discretion of the research team. If a participant has worsening of MDD but no immediate safety concern, we will recommend that the patient seek psychiatric consultation. If participants have questions regarding clinical care, they will be referred to a mental healthcare provider. If a participant does not have a mental healthcare provider, the investigators will help them to identify local resources. All participants will be given materials on local resources for psychiatric care and suicide hotline information. To ensure safe participation, subjects will be asked to identify an emergency contact and provide contact information so that the study team may contact these individuals in case of an emergency.

- MINI/PHQ-9/PROMIS: For the purposes of this study, we use these tests to identify potential subjects who have MDD (or not) and to identify for exclusion those who have psychiatric illness

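### The design statement names two groups, but the recruitment section adds 30 SSRI-treated adults whose place in the analysis is unspecified and whose drug exemption is not confined to them

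*Combined protocol and SAP*

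**What the plan says.** **Design.** Section 6 (Procedures) calls the study cross-sectional and states "Two subject groups will be recruited: 1) non-depressed healthy adults (HA"); the second group is unmedicated adults meeting DSM-5 criteria for MDD. It gives no group sizes. Section 4 (Special Populations) also describes the MDD participants as unmedicated, both in the form answer and in the text that follows.

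**Enrolment.** Section 7 (Study Population and Recruitment) lists 60 non-depressed healthy adults, then "60 unmedicated adults with MDD will meet the DSM-5 criteria for MDD", then, on its own line, "30 selective serotonin reuptake inhibitor (SSRI)-treated (current monotherapy) adults with MDD will meet the DSM-5 criteria for MDD". No total is printed.

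**Aims and analysis.** The three aims in section 5 refer to young-to-middle-aged adults with MDD and do not mention treatment status. Section 10 (Data) plans mainly multilevel models and multilevel structural equation models at p < 0.05. It names no group factor, contrast or pooling rule.

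**Eligibility.** Section 7 says "The exclusion criteria are applied to all groups". One item bars current or recent (within 8 weeks) use of two classes of drug: "medications that could conceivably alter neural-cardiovascular-immunological function", and "psychoactive or psychopharmacological drugs aside from SSRIs". Another lists "Changes or alterations in medication status (starting a new, additional, or different medication or changing the dose of a current medication"). Section 8 adds: "No patients with MDD who are currently treated with antidepressant pharmacotherapy will be asked or allowed to discontinue to participate".

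**The concern.** The document disagrees with itself on how many groups are enrolled and on whether treated patients are among them. Two things depend on the answer.

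The first is what the MDD results describe. The generic wording of the aims would admit the SSRI-treated adults, while the design statement would not. If the choice is left until the data are in hand, it can be made with the results in view.

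The second is how clean the groups are. The exemption is evidently there so that the 30 SSRI-treated adults can be enrolled, but as written it reaches all three groups. Recent SSRI exposure among unmedicated participants, or SSRI use among healthy ones, would blur the contrast between unmedicated MDD and healthy adults.

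**Working it through.** **1. Counts (section 7).** The plan prints no total and no sample-size derivation, so there is no figure to reproduce.
- All groups: 60 + 60 + 30 = 150.
- SSRI-treated share of enrolment: 30/150 = 20%.
- SSRI-treated share of those with MDD: 30/(60 + 30) = 30/90 = one third.

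**2. What pooling would do.** Let δ be the difference in an outcome mean, SSRI-treated minus unmedicated MDD. The pooled MDD mean is the unmedicated mean plus (30/90) × δ, a shift of δ/3. The documents give no value for δ.

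**3. Precision under each role.** This is a simple illustration with group means and a common SD; the planned models are multilevel. The standard error in SD units is √(1/n₁ + 1/n₂).
- Unmedicated MDD v healthy, 60 v 60: √(1/60 + 1/60) = 0.1826.
- Pooled MDD v healthy, 90 v 60: √(1/90 + 1/60) = 0.1667.
- SSRI-treated v either other group, 30 v 60: √(1/30 + 1/60) = 0.2236.
- Ratios: 0.1826/0.1667 = 1.095 and 0.2236/0.1826 = 1.225.

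The role given to the 30 thus changes both the quantity estimated and its precision.

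**4. Reading the eligibility rules together (sections 4, 7 and 8).**
- *Current SSRI use, unmedicated group.* Barred by the group's own label.
- *Recent SSRI use, unmedicated group.* The 8-week look-back belongs to the same item as the exemption, so the psychoactive-drug limb does not reach it. The rule in sections 4 and 8 concerns stopping an antidepressant in order to take part; it does not address someone who stopped recently for another reason.
- *SSRI use, healthy group.* The group is defined by absence of psychiatric illness. No medication criterion clearly bars an SSRI taken for a non-psychiatric reason.
- *Medication-change item.* It has no time window, and its parenthesis covers starting, adding, switching and dose changes without naming stopping.
- *Open-ended limb on neural, cardiovascular and immune effects.* It applies to all groups. If it covered SSRIs it would also exclude the 30 SSRI-treated adults.

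**5. Size of the eligibility gap.** If a share p of the 60 unmedicated participants had recent SSRI use and differed by δ′ from the rest, the group mean would move by p × δ′. The documents give no p. Purely as an assumption, p from 5% to 20% would be 3 to 12 of 60 people and a shift of 0.05δ′ to 0.20δ′.

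**The case against.** The best defence is that section 7 sets out three distinct groups with counts, that the word unmedicated already keeps current SSRI users out of the second, and that investigators may exclude anyone at their discretion. The medication-change item can also be read to include stopping a drug, and the bracketed examples after the exemption name antidepressants. On this view only one sentence in section 6 is out of date.

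Part of this stands. Current SSRI use in the unmedicated group is barred. But discretion is not a criterion, the medication-change item has no window, and the bracketed antidepressants are governed by the exemption that precedes them. The gap is not reliably closed.

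A reader might infer more than the documents support:
- *That the protocol states a size of 120 and contradicts it.* It does not. Section 6 gives no numbers; the conflict is over the number and definition of groups.
- *That the SSRI-treated group has no role.* The aims' wording can include it. Its role is unspecified, not absent, and section 10 names no groups of any kind.
- *That a third group brings a known inflation of false positives.* The plan names no pairwise tests of group means, and freedom to choose a comparison would exist with two groups.
- *That the added testing cycles and payments measure the defect.* These are ceilings, since section 6 lets participants decline procedures or the second cycle, and they say nothing about validity.
- *That section 6 makes unmedicated MDD versus healthy the primary comparison.* It lists who is recruited and names no primary comparison.

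**Conclusion.** The contradiction is in the current text and needs no assumption: two groups in section 6, three in section 7, with section 4 describing the MDD participants as unmedicated. The 30 SSRI-treated adults are 20% of the 150 listed and one third of those with MDD, and nothing says how they enter the analysis. Followed as written, the exclusions in section 7 can admit recent SSRI users to the unmedicated group and SSRI users to the healthy group.

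How often that would happen is unknown, so no bias can be quantified. The δ/3 shift is arithmetic on the listed counts. The standard-error ratios rest on equal variances and simple means. The point must be fixed because it governs who is enrolled and who is compared, and correcting the text is cheap.

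**What to change.** Reconcile sections 4, 6 and 7.

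**If the SSRI-treated group is intended:**
- In section 6, state three groups with their counts, and align section 4.
- In the section 7 exclusions, confine the SSRI exemption to the SSRI-treated group, and reconcile how the existing look-back applies to SSRIs in the other two. That rule is the sponsor's choice.
- In section 10, make SSRI-treated MDD a separate level of the group factor rather than pooling it with unmedicated MDD. State before analysis which MDD participants enter each of Aims 1 to 3 and which group comparison is primary.

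**If it is not intended:** remove the group from the section 7 list and the exemption from the exclusions.

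**Cost.** Wording changes, plus a check that consent and recruitment materials match. In section 15 the consent file label is dated 20240503 and the protocol label 20240701. Two recruitment files are labelled unMDD, while the ResearchMatch file carries the protocol's date. Their contents are not visible here, so this is only a prompt to check. If the two MDD groups are in fact alike, not pooling leaves the standard error against healthy adults about 9.5% larger than with 90 v 60, on the simple equal-variance calculation above. Removing the group would lower listed enrolment by 30 of 150.
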